### **2.3. Dengue case detection**

Suspected cases in the study may arise from two sources:

1. Through enhanced passive surveillance
2. As a result of active surveillance between scheduled visits

#### **2.3.1. Case detection through enhanced passive surveillance**

- This form of surveillance was key in maximising the likelihood to detect SDC early, during the course of illness. Study personnel instructed subjects/subject's parent(s)/LAR(s)/ designate (if applicable) to contact the study personnel or come to a designated study healthcare centre/hospital for medical evaluation in case of febrile illness (preferably within 5 days of onset of febrile illness).

#### **2.3.2. Case detection through active surveillance**

Between scheduled visits, detection of SDC in the cohort were performed using active surveillance of acute febrile illness and enhanced passive surveillance.

- **Active surveillance:** Households were contacted regularly to enquire about the occurrence of febrile illness among the study subjects. Preferably, the frequency of contacts was once per week. In sites with marked dengue seasonality, the frequency of contact may have been twice per month during periods of low transmission of dengue. These periods may have been modified upon decision of the central study team based on available epidemiological information. The mode of contact may have included phone calls and/or house visits. In addition to the regular phone contact, some sites may have opted to check the school absenteeism log and contact the household of the children who are absent.

- If febrile illness was identified during active surveillance, an appointment was arranged at the designated study healthcare centre/ hospital as soon as possible (preferably within 5 days following the onset of symptoms).

*A household visit may have been planned if the subject cannot come to the designated healthcare centre/hospital. This situation should have, however, remained exceptional.*

## 2.4. Dengue seasons

Dengue season:

Study site number	Study site name	Dengue season 2017, 2018
219902	Mexico	1st July to 30th October of each year
219497	Philippines	1st May to 30th November of each year

## 3. OBJECTIVES

### 3.1. Primary objective

- To estimate the overall incidence rate of reverse-transcriptase quantitative polymerase chain reaction (RT-qPCR)-confirmed symptomatic DENV infection in a multi-centre cohort of household members aged 6 months to 50 years.

### 3.2. Secondary objectives

- To estimate the incidence rate of virologically confirmed (through RT-qPCR or NS1) and probable (based on serological evidence) symptomatic DENV cases, separately and combined - by age, gender, site, serotype (if applicable) and anti-DENV IgG serological status at enrolment.
- To estimate the prevalence of anti-DENV immunoglobulin G (IgG) antibodies against dengue in the study population, overall and by age and site (at enrolment), for all participants and among dengue cases (confirmed and probable).
- To describe clinical presentations of dengue cases (confirmed and probable).

### 3.3. Tertiary objectives

- To describe the spatial and temporal distribution of dengue cases (confirmed and probable) among cohort participants in the study areas and analyse determinants of spatio-temporal transmission (e.g. environmental, entomological, socio-demographic or ecological factors).
- To describe the DENV, and other flaviviruses (i.e. Japanese Encephalitis Virus [JEV; mostly relevant in Southeast Asia]) or West Nile Virus [WNV; mostly relevant in Latin America]) neutralising antibody profile in a subset of subjects.
- To explore other infectious aetiologies than dengue in subjects with episodes of febrile illness referred to as “suspected dengue case” (chikungunya, Zika, influenza, leptospirosis).

- To explore determinants of past dengue infection and dengue illness.
- To further characterise the immune status at enrolment (e.g. antibody avidity, etc.).

Tertiary objectives will not be analysed (refer to Section 10).

## **4. ENDPOINTS**

### **4.1. Primary endpoint**

- RT-qPCR confirmed symptomatic DENV infection (all DENV types) during the study period.

### **4.2. Secondary endpoints**

- DENV-type specific confirmed symptomatic DENV infection.
- Virologically confirmed (by RT-qPCR or NS1) and probable (based on serological evidence) symptomatic DENV infection.
- Status for anti-DENV IgG at enrolment (indicative of past DENV infection).
- Symptoms and severity of symptomatic dengue.

### **4.3. Tertiary endpoints**

Exploratory objectives may be assessed based on, but not limited to the following endpoints:

- Spatial coordinates of the houses of participating households and of dengue cases and date of symptoms onset (applicable only for symptomatic cases).
- Neutralising antibodies titres against DENV 1-4.
- Neutralising antibody titres against other flaviviruses (such as JEV and WNV).
- Other infectious aetiology than dengue in subjects with episodes of febrile illness referred to as “suspected dengue cases” (chikungunya, Zika, influenza, leptospirosis).
- Determinants of past dengue infection and dengue illness.
- Characteristics of immune status against DENV infection.

## 5. ANALYSIS SETS

### 5.1. Definition

The following analysis sets are defined:

Analysis Set	Description
Total cohort	All subjects enrolled in the study
Total cohort without subjects with code 900	All subjects from the Total cohort without elimination codes 900
ATP cohort	All subjects from the Total cohort without subjects with code 900 and who met all inclusion/exclusion criteria

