### 10.3.2. According-To-Protocol (ATP) cohort

The ATP cohort will include all evaluable subjects, that is, subjects who meet all eligibility criteria, complying with the procedures defined in the protocol and for whom data of at least one follow-up contact are available. The surveillance period for one subject will be defined as the duration from the date of enrolment until the date of the last follow-up contact for this subject. Reasons for elimination from ATP analyses will be established at the time of data cleaning and documented.

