## **10.7. Analysis of primary objective**

The primary analysis will be based on the ATP cohort. If the percentage of enrolled subjects with serological results excluded from the ATP cohort is 5% or more, a second analysis based on the Total cohort will be performed to complement the ATP analysis.

The following analyses will be performed:

Incidence rate of RT-qPCR confirmed symptomatic dengue infection with 95% CI: the numerator will be the number of subjects with RT-qPCR confirmed symptomatic dengue infection during the study period. The denominator will be the total person-years at risk, i.e., from enrolment until the first RT-qPCR confirmed symptomatic dengue infection during the entire study period.

CIs for incidence rates and prevalence will account for clustering of observations within households for the analyses by centre and also the stratification by centres for the overall analyses. Details of the methods will be described in the statistical analysis plan (SAP).

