#### 5.2.2. Elimination from ATP cohort

Code 900 (invalid informed consent or fraudulent data) and code 2010 (Protocol violation linked to the inclusion/exclusion criteria) will be used for identifying subjects eliminated from ATP cohort.

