### 7.4. Analysis of incidences

The analyses will be performed on the ATP cohort.

The following analyses will be performed by study site and overall:

- Incidence proportion of RT-qPCR confirmed symptomatic dengue infection during the study period.
- Incidence proportion of virologically confirmed symptomatic dengue infection during the study period.
- Incidence proportion of probable symptomatic dengue infection during the study period.
- Incidence proportion of virologically confirmed or probable symptomatic dengue infection during the study period.
- The numerator will be the number of subjects with at least one specified event reported during the study period. The denominator will be the number of subjects in the ATP cohort.

95% CI accounting for clustering effect will be computed on all estimated incidence proportions. The method for estimating the CIs is described in Section 12.1.

- The proportion, with 95%CI, of subjects with Dengue Virus Ab.IgG positive result (ELISA) at Visit 1 will be tabulated by study site and age category.

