## 10. CHANGES FROM PLANNED ANALYSES

The cohorts were clarified and the Total cohort without subjects with code 900 was added.

Due to study termination:

- Medical history and vaccination history for Japanese Encephalitis and Yellow Fever will not be summarised.
- Tertiary objectives will not be analysed.
- Refer to Section 7 for the laboratory tests performed. Those not performed will therefore not be analysed. In addition, no GMTs will be computed as only qualitative laboratory results (positive/negative) will be available.
- Incidence proportions will be computed instead of incidence rates for the primary and secondary objectives. Sub-analyses by season/year, by age category, gender, serotype and dengue serological status at the beginning of the analysis period will not be performed due to the low number of virologically confirmed or probable symptomatic dengue infection reported during the study period. In addition, analysis of incidences will only be performed on the ATP cohort.
- The proportion of subjects with Dengue Virus Ab.IgG positive result (ELISA) at Visit 1 will not be summarized among dengue cases (confirmed and probable) due to the low number of virologically confirmed or probable symptomatic dengue infection reported during the study period.
- The statistical methodology to estimate the CI for proportions accounting for clustering effect will not use stratification by center for the analyses on overall centers (refer to Section 12.1).

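### The SAP's ATP cohort drops the protocol's follow-up-contact and procedure-compliance conditions without naming them, so an eligible subject never contacted after enrolment counts as a full non-case in the primary incidence proportion

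*SAP*

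**What the plan says.** Protocol Section 10.3.2 sets three conditions for the ATP cohort: eligibility, compliance with protocol procedures, and being a subject "for whom data of at least one follow-up contact are available". The same section ties observation time to contact: the surveillance period is "defined as the duration from the date of enrolment until the date of the last follow-up contact". Protocol Section 10.7 then uses time at risk for the primary analysis: "The denominator will be the total person-years at risk, i.e., from enrolment until the first RT-qPCR confirmed symptomatic dengue infection".

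SAP Section 5.1 gives the ATP cohort as "All subjects from the Total cohort without subjects with code 900 and who met all inclusion/exclusion criteria". SAP Section 5.2.2 confirms that only two codes remove a subject: code 900 (invalid consent or fraudulent data), and "code 2010 (Protocol violation linked to the inclusion/exclusion criteria) will be used for identifying subjects eliminated from ATP cohort". No code covers absence of follow-up or non-compliance with procedures.

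SAP Section 7.4 computes incidence proportions on this cohort: "The denominator will be the number of subjects in the ATP cohort". SAP Section 10 discloses the change of measure: "Incidence proportions will be computed instead of incidence rates for the primary and secondary objectives". On the cohorts it says only: "The cohorts were clarified and the Total cohort without subjects with code 900 was added".

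**The concern.** Under person-time, the contact condition hardly matters for incidence. A subject with no contact after enrolment has a surveillance period of zero and adds nothing to the denominator, whether kept or excluded. Under a head count it does matter. Such a subject adds one to the denominator and cannot enter the numerator, because a case has to be seen to be detected. The SAP moved to a head count and, in the same document, removed the condition that would have kept never-observed subjects out.

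Two things are at stake. The primary proportion can be shifted, and only downwards. And a reader who knows the protocol's definition will take ATP to mean something it no longer means.

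The outputs described in the SAP would not reveal the number affected. The exclusion table in SAP Section 7.1 has no code for it. The withdrawal table normally gives only an upper bound, because Protocol Section 9.2 counts as a withdrawal anyone not available for the concluding visit, however often they were contacted before. An analysis on the Total cohort would contain the same subjects.

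**Working it through.** **Inputs.** Enrolled: 350 in Mexico (Visits 1 to 3, 24 months) and 500 in the Philippines (Visits 1 to 2, 12 months), total N = 850 (SAP Sections 2.1 and 7). Dropout 5% per year, overall incidence 7.1 per 1000 person-years, design effect 1.8 (Protocol Section 10.2). Neither k, the number with no contact after enrolment, nor the number of cases is given; both are assumed below. N = 850 also assumes that no subject is removed under code 900 or 2010.

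**The plan's own figures.** Person-years for 1750 subjects, averaging the start and end of each year: (1750 + 1662.5)/2 + (1662.5 + 1579.4)/2 = 3327, as stated. Cases: 3327 × 7.1/1000 = 23.6, stated as about 24. The intervals also reproduce: exact Poisson 4.5 to 10.6, and normal with design effect 3.3 to 10.9.

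**Case count for illustration.** The same method for the subjects enrolled:
- Mexico: (350 + 332.5)/2 + (332.5 + 315.9)/2 = 665.4 person-years, × 7.1/1000 = 4.7 cases.
- Philippines: (500 + 475)/2 = 487.5 person-years, × 7.1/1000 = 3.5 cases.
- Total: 1152.9 person-years, 8.2 cases. I take 8, split 5 and 3.

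**Effect of the dropped contact condition.** With x cases, the SAP gives x/N and the contact condition gives x/(N - k). The ratio is (N - k)/N = 1 - k/N, whatever x is.

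**Largest k compatible with the planned dropout.** A subject who completes year 1 has been contacted, so only first-year dropouts could lack any contact:
- Mexico: 350 × 0.05 = 17.5
- Philippines: 500 × 0.05 = 25
- Total: 42.5, and 42.5/850 = 5.0%

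| | SAP rule | With contact condition |
|---|---|---|
| Overall, k/N = 1% | 8/850 = 0.94% | 8/841.5 = 0.95% |
| Overall, k/N = 5% (bound) | 8/850 = 0.94% | 8/807.5 = 0.99% |
| Mexico, at the bound | 5/350 = 1.43% | 5/332.5 = 1.50% |
| Philippines, at the bound | 3/500 = 0.60% | 3/475 = 0.63% |

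**Against sampling error.** Logit interval for 8/850 with design effect 1.8: the logit is -4.656 and its SE is √(1.8/(8 × 0.9906)) = 0.477, giving 0.37% to 2.36%. The largest shift, 0.05 percentage points, is small beside this. It can still change the printed figure: at the SAP's two decimals and with 8 cases, k = 4 already does so (8/846 = 0.95%).

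**The case against.** The strongest reply is that the effect is probably close to nil. Households had to be reachable by phone (Protocol Section 6.3), contacts were preferably weekly or else twice monthly in low season, and failed attempts led to a home visit (Protocol Section 7.5.3). Nothing in the documents shows that k exceeds zero. This stands, and it limits the weight of the point.

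A reader might infer a larger bound by treating every planned withdrawal as never contacted: 350 × (1 - 0.95²) + 500 × 0.05 = 34.1 + 25 = about 59, or 7.0% of 850. The documents do not support that. About 16.6 of the Mexican withdrawals (332.5 × 0.05) fall in year 2, among subjects whom Protocol Section 10.2 counts as having completed year 1. Even 42.5 is generous, since the plan's person-year calculation credits first-year dropouts with half a year on average.

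A reader might also infer that the cohort change was concealed. It was not: SAP Sections 5.1 and 5.2.2 state the new definition openly, and SAP Section 10 says that the cohorts were touched. Protocol Section 10.3.2 leaves the reasons for elimination to data cleaning, Protocol Section 10.11 places deviations in the final report, and neither that report nor the table templates are available here. What remains is narrower. The SAP fixes the codes as 900 and 2010 only, and dropping two membership conditions is more than a clarification.

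Finally, the protocol does not define its follow-up contact. In its Tables 2 and 4 the term denotes the contact about 21 days after a suspected-dengue visit. That cannot be meant here, since it would restrict the ATP cohort to subjects with such a visit. Any workable rule is therefore an operational reading, not a restoration of exact wording.

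**Conclusion.** The point holds. The SAP drops two of the protocol's three ATP conditions, names neither, and counts an eligible subject with no contact after enrolment as a full non-case in the primary proportion. Relative to the contact condition, the direction is certain: lower or unchanged, by the factor 1 - k/N.

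The size cannot be established, because k is not given and may be near zero. At the planned dropout the relative lowering is at most about 5.0%: 0.94% instead of 0.99% with an assumed 8 cases, against a CI of 0.37% to 2.36%. This would not change the reading of the study. It is worth correcting because the shift goes one way, affects the primary analysis and is cheap to remove.

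A reader might infer that reinstating the condition yields the true incidence. It does not. A subject contacted once in the first week still counts in full, and Mexico's 24 months and the Philippines' 12 months still count alike. Those are separate consequences of the head count, which SAP Section 10 discloses.

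**What to change.** For the incidence denominator in SAP Section 7.4 only, require at least one documented contact after enrolment: Visit 2 or Visit 3 (including by telephone), an ad-hoc visit, or a recorded last-contact date after Visit 1. State that this is an operational reading of the protocol's term. Keep the wider set for Visit 1 demographics and IgG prevalence, where follow-up is irrelevant. Report k by site. In SAP Section 10, name both dropped ATP conditions, follow-up contact and procedure compliance, and give the reason for each.

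The cost is one derived date, one elimination code and a slightly smaller denominator. No case is lost, because every detected case has a contact. There is one real downside: routine surveillance contacts need no eCRF entry (Protocol Table 2), so a few non-cases who were under surveillance might have no recorded contact and be excluded, which would raise the proportion. Show the proportion on the wider set alongside, so that the reader can see the difference. If k is zero, one sentence saying so closes the matter for the contact condition.

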### 5.2. Criteria for eliminating data from Analysis Sets

Elimination codes are used to identify subjects to be eliminated from analysis. Detail is provided below for each analysis set.

#### 5.2.1. Elimination from Total cohort without subjects with code 900

Code 900 (invalid informed consent or fraudulent data) will be used for identifying subjects eliminated from Total cohort without subjects with code 900.

#### 5.2.2. Elimination from ATP cohort

Code 900 (invalid informed consent or fraudulent data) and code 2010 (Protocol violation linked to the inclusion/exclusion criteria) will be used for identifying subjects eliminated from ATP cohort.

### 5.3. Important protocol deviation not leading to elimination from Analysis set

Refer to the Periodic Review of Protocol deviation documents stored in C.A.R.S./Epidemiology/DENGUE/Studies/007 BOD/05 Site Management/05.04 Site Management/05.04.06 Protocol Deviations.

## **6. DENGUE CASE CLASSIFICATION**

The following classification of suspected dengue case (SDC) was used in this study.

### **6.1. Suspected symptomatic dengue case**

Acute febrile illness measured as  $\geq 38.0^{\circ}\text{C}$  with a thermometer by any route or recent history of febrile illness (onset in the past 8 days) reported by the subject/the parent(s)/LAR(s)/ designate (if applicable) of the subject for at least two consecutive days (a duration of approximately 36-48 hours) and of less than 7 days duration, which may be accompanied by other dengue symptoms or signs and does not have a defined focus or an obvious reason unrelated to dengue (based on physician judgement).

Note: Besides fever, other dengue associated signs and symptoms include but are not limited to: upper respiratory tract symptoms like cough, nasal congestion, runny nose and dyspnoea, gastrointestinal symptoms and febrile convulsion in infants/older children and fatigue, headache, pain behind the eyes, abdominal pain, nausea, vomiting, muscle ache, joint ache, diffuse rash on the trunk, itching of skin (pruritis) in adults/adolescents.

A number of infectious and non-infectious diseases mimic dengue and severe dengue. Physicians should be careful not to rule out dengue diagnosis too quickly, when the differential diagnosis cannot be accurately made. Early symptoms of dengue may include gastrointestinal and upper respiratory symptoms and may be misdiagnosed as diarrhoeal diseases or other diseases with flu-like symptoms. The WHO handbook for clinical management of dengue provides a list of conditions that mimic the febrile phase and the critical phase of dengue infection.

A SDC presenting at the health care facility within 5 days following the onset of symptoms (i.e. day of symptoms onset and the next 4 days) will be defined as an 'early presenter'. A SDC presenting at the health care facility 6 days or more after the onset of symptoms will be defined as 'late presenter'. Both early and late presenters will have a scheduled visit at the study healthcare centre including blood sampling for laboratory diagnosis.

Seven consecutive calendar days without fever (body temperature  $\geq 38.0^{\circ}\text{C}$ ), in the absence of antipyretic medication, are required to separate two episodes of SDC.

### **6.2. Laboratory confirmation**

#### **6.2.1. RT-qPCR confirmed symptomatic DENV infection**

A SDC confirmed by RT-qPCR

#### **6.2.2. A virologically confirmed symptomatic DENV infection**

A SDC confirmed by RT-qPCR or NS1.

**6.2.3. Probable dengue case**

A SDC with:

- DENV RT-qPCR negative or not performed (late presenter)
- and
- DENV NS1 negative or undetermined (early or late presenter)
- and
- Anti-DENV IgM positive with a rapid immunochromatographic (ICT) assay or an ELISA assay
- Or
- Anti-DENV IgG positive (rapid ICT assay or ‘capture ELISA’ assay)

**7. STATISTICAL ANALYSES**

SAS software will be used for statistical analysis.

Note that data derivation rule and statistical methods are described in Section 12 and will not be repeated below.

Continuous variables will be summarized with number of non-missing observations, mean, standard deviation (SD), median, minimum, maximum, 25th and 75th percentiles. Categorical variables will be summarized with frequency tables; numbers and percentages for each level will be given.

If an elimination code 900 is attributed, then all the analyses planned to be done on the Total cohort will be done on the Total cohort without subjects with code 900, except Template 5 from EPI-DENGUE-007 BOD (200318) TFL (24-MAY-2019) DRAFT.

The final analysis will be performed on the following study sites using data up to the specified study visits covered up to study termination:

Study sites name	Number of enrolled subjects	Study visits covered at study termination	Dengue season covered at study termination
Mexico	350	Visit 1 to Visit 3	2017, 2018
Philippines	500	Visit 1 to Visit 2	2018

The laboratory results (POS/NEG/IR=invalid result/EQV=equivocal (i.e. level of measured Dengue IgG Ab is not enough to conclude of a Dengue infection)) will be available at the scheduled visits for the following tests:

- Dengue Virus Ab.IgG by ELISA (v\_id= 3789.005) will be available at Visit 1 for Mexico site
- Dengue Virus Ab.IgG by ELISA (v\_id= 3789.005) will be available at Visit 1 and 2 for Philippines site

The laboratory results (POS/NEG/IR) will be available in case of SDC, at first visit, for the following tests:

Assays	Method	Early presenters	Late presenters
DENV RT-qPCR: 
 
• Dengue Virus Type 1 RNA (v_id= 3415.005)
 
• Dengue Virus Type 2 RNA (v_id= 3415.006)
 
• Dengue Virus Type 3 RNA (v_id= 3415.007)
 
• Dengue Virus Type 4 RNA (v_id= 3415.008)
 
	RT-qPCR	Yes	Yes
DENV NS1	RAPIDIMM	Yes	Yes
Anti-DENV IgM	RAPIDIMM	Yes	Yes
Anti-DENV IgG	RAPIDIMM	Yes	Yes
Hematology / Biochemistry		Yes	Yes

RAPIDIMM = rapid immunochromatographic assay

